Aimovig® [erenumab (EREN)] is a first in class FDA-approved human monoclonal antibody (UmAb) for the prevention of migraine in adults. It selectively targets and blocks the calcitonin gene-related peptide (CGRP) receptor, disrupting a key component of migraine pathophysiology (Hargreaves & Olesen, 2019). Several studies have provided evidence of the safety and efficacy of Aimovig® in reducing the frequency of migraine compared to placebo (Goadsby et al., 2017; Tepper et al., 2017). Furthermore, an open-label longer-term study found that Aimovig® was safe and well-tolerated with a safety profile consistent with shorter-term placebo-controlled studies (Ashina et al., 2020), through 5-years of treatment. Aimovig® has rapidly become a widely accepted prescription drug for the prevention of migraines, including episodic migraine and chronic migraine (CM) along with other anti-CGRP monoclonal antibody-based therapies (Yuan et al., 2019).

Temporomandibular Disorders (TMD) are known to be co-morbid with the medical diagnosis of CM (Speciali, 2015). TMD symptoms are numerous and chronic in nature (see appendix A) and TMD treatments are more numerous than symptoms and are predictable only in their unpredictability (see Appendix B). Most patients experiencing TMD find it to be a chronic, untreatable condition. In the US alone, TMDs are the second most commonly occurring musculoskeletal conditions resulting in pain and disability (after chronic low back pain), affecting approximately 5 to 12% of the population, with an annual cost estimated at \$4 billion (NIH/NIDCR). There is increasing interest in the concept of Chronic Overlapping Pain Conditions (COPCs), which include TMD, fibromyalgia, irritable bowel syndrome, vulvodynia, myalgic encephalomyelitis/chronic fatigue syndrome, interstitial cystitis/painful bladder syndrome, endometriosis, chronic tension-type headache, migraine headache, and chronic lower back pain that may have common biopsychosocial factors (Maixner et al., 2016).

2.1 Primary Objective and Outcome Measure

To assess the effects of Aimovig® (EREN) compared to placebo (EREN-P) based on the change in mean between-group difference in pain using the Brief Pain Inventory (BPI) 4-item pain severity/intensity scale during the 20-week trial. The BPI is a validated and widely used outcome measures in chronic pain trials (Kean et al., 2016; Kroenke et al., 2019). *We postulated that Aimovig® will be superior to placebo in reducing pain intensity/severity over 20 weeks.*

2.2 Secondary Objective and Outcome Measures

To assess the effects of Aimovig® (EREN) compared to placebo (EREN-P) based on the change in mean between-group difference in secondary outcomes during the 20-week trial and after 24 weeks (two months after the last treatment). The outcome measures are based on consensus recommendations for research assessments in chronic pain and TMD research (Ohrbach et al., 2016; Kroenke et al., 2019). *We postulated that Aimovig® will be superior to placebo in improving several secondary outcomes including:*

- a) Pain interference as measured by the BPI interference scale
- b) Trajectory of pain improvement based on changes in daily reporting of pain using the PEG (Pain, Enjoyment, General Activity) Scale as measured using an app downloaded on the subject's smartphone or for individuals without smartphones at baseline and every 4 weeks over the 24-week study period
- c) Days of use of TMD pain-specific medication per month
- d) Global improvement in pain as measured by the Patient Global Impression of Change (PGIC)
- e) Jaw function as measured by the Jaw Function Limitation Scale (JFLS-8)
- f) Depressive and anxiety symptoms as measured by the Patient Health Questionnaire (PHQ-4)
- g) Somatic symptom severity as measured by the Somatic Symptoms Scale (SSS-8)
- h) Safety and tolerance as measured by incidence of AEs and SAEs

3. Study Design

This was a 24-week, randomized, double-blinded, placebo-controlled, parallel group proof-of-concept study with two arms (active and placebo). The plan was to enroll 30 subjects. There was a four-week screening period to identify subjects that meet the diagnostic criteria (DC/TMD) for "myalgia", recommended by the International RDC/TMD Consortium Network and Orofacial Pain Special Interest Group (Schiffman et al., 2014). The Diagnostic Criteria for Temporomandibular Disorders Symptom Questionnaire and DC/TMD Examination Form (Ohrbach, 2016) was used during Screening and Baseline visits to confirm the TMD diagnosis and determine whether subjects met the inclusion/exclusion criteria.

Subjects attended a Screening visit followed by Baseline visit to randomize eligible subjects to active (EREN) or placebo (EREN-P). During the Baseline visit and Wks 4, 8, 12, and 16, subjects received treatment with either 140 mg of EREN or Placebo administered by subcutaneous injection. At Baseline and Wks 4, 8, 12, 16, 20, and 24 subjects were instructed to complete the Brief Pain Inventory (BPI) (Kean et al., 2016); PEG (Pain, Enjoyment, General Activity) Scale (Krebs et al., 2009); pain mediation assessment; Patient Global Impression of Change (PGIC)

(Kroenke et al., 2018) (except for Baseline visit); Jaw Function Limitation Scale (JFLS) (Ohrbach et al., 2008); Patient Health Questionnaire (PHQ-4) (Kroenke et al., 2009); and Somatic Symptom Scale (SSS-8) (Toussaint et al., 2017). These visits also included review of continuance criteria and adverse event collection.

At the Screening and Baseline visits the subjects were instructed on how to use the PEG Scale and pain use assessment app, which was downloaded on their smartphone, to provide a daily assessment of their pain intensity and interference with enjoyment and general activity (PEG) and their daily used of pain medications. Subjects who did not own a smartphone or were unwilling to use the app on a daily basis only completed the PEG and pain medication assessment at the Baseline visit and all subsequent visits using the app onsite.

4. Study Population

The study population consisted of male and female subjects diagnosed as having pain-related TMD using the diagnostic criteria (DC/TMD) for “myalgia”, recommended by the International RDC/TMD Consortium Network and Orofacial Pain Special Interest Group (Schiffman et al., 2014). The goal was to recruit 30 subjects that fulfill the inclusion and exclusion criteria. It was anticipated that 24 subjects (12 in each treatment group) will complete all aspects of the study.

4.1 Inclusion Criteria

Subjects eligible for inclusion in the study must have met all of the following criteria:

1. Signed the informed consent;
2. Have a history of head, face, neck and/or shoulder pain for longer than 3 months;
3. Have a diagnosis of myalgia based on clinical examination using DC/TMD criteria;
4. Age 18 years and younger than 60 years;
5. Have a good knowledge of the English language;
6. Able to understand and comply with the study requirements; and
7. If taking prescription pain medications, the dose regimen must be stable for at least 2 months prior to the screening visit.

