| Study drug administration | | X | X | X | X | X | | |
| Inclusion / Exclusion criteria | X | | | | | | | |
| Demography | X | | | | | | | |
| Medical history/current medical conditions | X | | | | | | | |
| Prior therapy for TMD | X | | | | | | | |
| Adverse Events | X | X | X | X | X | X | X | X |
| Concomitant medications | X | X | X | X | X | X | X | X |
| Familiarize with PEG App | X | X | | | | | | |
| BPI, PEG and pain medication assessment (daily), JFLS-8, PHQ-4, SSS-8 | | X | X | X | X | X | X | X |
| PGIC | | | X | X | X | X | X | X |

Screening Visit: Subjects will complete the informed consent process, being given ample time to review the consent and to ask any questions they have before deciding if they wish to participate. Those interested will sign and date their informed consent and the consent will also

be signed and dated by the person reviewing the consent process with them. Subjects will receive a signed copy of their consent before leaving this visit. A Study Dentist qualified to diagnosis TMD will review the potential subject's health history, medications and TMD history for the inclusion and exclusion criteria.

The Diagnostic Criteria for Temporomandibular Disorders Symptom Questionnaire (Appendix C) and DC/TMD Examination Form (Ohrbach, 2016) will be used to confirm the TMD diagnosis and determine whether subjects meet the inclusion/exclusion criteria. To meet the diagnostic criteria for TMD Myalgia (ICD-9 729; ICD-10 M79.1) (Schiffman et al., 2014), subjects must have a history of pain of muscle origin that is affected by jaw movement, function, or parafunction, and demonstrate replication of this pain with provocation testing of the masticatory muscles. The specific criteria (Schiffman et al., 2014) include having a positive history for both pain in the jaw, temple, in the ear, or in front of ear and pain modified with jaw movement, function or parafunction. During clinical examination, subjects must have a confirmation of pain in the temporalis or masseter muscle(s) and report familiar pain in the temporalis or masseter muscle(s) with at least one of the following provocation tests: palpation of the temporalis or masseter muscle(s) or maximum unassisted or assisted opening movement(s).

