Appendix C – Diagnostic Criteria for Temporomandibular Disorders Symptom Questionnaire

Patient name _____ Date _____

PAIN

1. Have you ever had pain in your jaw, temple, in the ear, or in front of the ear on either side? No Yes

If you answered NO, then skip to Question 5.

2. How many years or months ago did your pain in the jaw, temple, in the ear, or in front of the ear first begin? _____ years _____ months

3. In the last 30 days, which of the following best describes any pain in your jaw, temple, in the ear, or in front of the ear on either side? No pain Pain comes and goes Pain is always present

Select ONE response.

If you answered NO to Question 3, then skip to Question 5.

4. In the last 30 days, did the following activities change any pain (that is, make it better or make it worse) in your jaw, temple, in the ear, or in front of the ear on either side?

| | No | Yes |
|--|--------------------------|--------------------------|
| A. Chewing hard or tough food |  |  |
| B. Opening your mouth, or moving your jaw forward or to the side |  |  |
| C. Jaw habits such as holding teeth together, clenching/grinding teeth, or chewing gum |  |  |
| D. Other jaw activities such as talking, kissing, or yawning |  |  |

HEADACHE

5. In the last 30 days, have you had any headaches that included the temple areas of your head? No Yes

If you answered NO to Question 5, then skip to Question 8.

6. How many years or months ago did your temple headache first begin? _____ years _____ months

7. In the last 30 days, did the following activities change any headache (that is, make it better or make it worse) in your temple area on either side?

| | No | Yes |
|--|--------------------------|--------------------------|
| A. Chewing hard or tough food |  |  |
| B. Opening your mouth, or moving your jaw forward or to the side |  |  |
| C. Jaw habits such as holding teeth together, clenching/grinding, or chewing gum |  |  |
| D. Other jaw activities such as talking, kissing, or yawning |  |  |

JAW JOINT NOISES

Office use

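### Entry requires no minimum TMD pain score and the BPI is not taken at Screening, so subjects with little room to improve on the primary outcome can be randomised and dilute the treatment difference

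*Combined protocol and SAP*

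**What the plan says.** Section 2.1 makes the BPI 4-item severity scale the primary outcome and postulates that the drug "will be superior to placebo in reducing pain intensity/severity over 20 weeks".

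Entry under Section 4.1 rests on two pain-related criteria. One is a duration: "Have a history of head, face, neck and/or shoulder pain for longer than 3 months". The other is a diagnosis: "Have a diagnosis of myalgia based on clinical examination using DC/TMD criteria". Section 6 (Screening Visit) spells out the diagnosis: a positive pain history, pain modified by jaw use, and on examination "confirmation of pain in the temporalis or masseter muscle(s) and report familiar pain" under provocation. Each element is present or absent. The Appendix C pain item ("In the last 30 days, which of the following best describes any pain in your jaw, temple") offers no pain, intermittent pain or constant pain, with no intensity rating. Nothing in Section 4.2 refers to a pain score for TMD.

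In the Section 6 schedule, the row "BPI, PEG and pain medication assessment (daily), JFLS-8, PHQ-4, SSS-8" is ticked from Baseline onwards and not at Screening. Baseline is also the day of randomisation and first dose. Continuance criteria are mentioned in Sections 3 and 6 but not defined or tied to a pain score. Randomisation is stratified by gender only (Section 5.3), and the MMRM lists group, time, their interaction and gender (Section 8).

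**The concern.** The screening period selects for a diagnosis, while the trial measures an intensity. The two can come apart. The symptom questionnaire looks back 30 days. The BPI severity items in Appendix D ask for worst and least pain in the last week, average pain and pain at this moment. Someone with intermittent jaw pain can satisfy the diagnosis and still score low. Stable prescription analgesics (inclusion criterion 7) and established oral orthotics (the exception in exclusion criterion 7) are allowed, so subjects with partly controlled pain may enter.

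A subject who starts at 1 or 2 can fall by at most 1 or 2 points. In a trial planned on 12 completers per group and a between-group effect of 1.2 SD, one or two such subjects per group matter. The design neither limits nor stratifies them, and baseline BPI is not a listed covariate.

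**Working it through.** **1. The plan's own figure (Section 8.1).** Two-sample t-test, n = 12 per group, two-sided 5%, d = 1.2. Degrees of freedom 2n − 2 = 22; noncentrality d√(n/2) = 1.2 × √6 = 2.94. Exact power is 80.2%, which agrees with the stated 80%. Enrolling 15 per group allows for 20% dropout (12/0.80 = 15). The sample-size arithmetic is sound.

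**2. A low score is possible under the rules.** Take a 0–10 item scale (assumed; the graphic is not shown) and intermittent pain rated worst 4, least 0, average 2, now 0. Severity = (4 + 0 + 2 + 0)/4 = 1.5. No criterion excludes this person on score.

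**3. How many, and what a cut would do.** The documents give no baseline mean or SD, so three normal baselines are assumed. The shares below 2 and 3 use the normal restricted to 0–10. For the means, out-of-range scores are capped, the Screening–Baseline reliability is taken as 0.8, and selection is on a Screening score of at least 3. The value 3 is only an illustration.

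| Assumed baseline mean (SD) | Below 2 | Below 3 | Mean Baseline score, no cut | With cut | Gain | Retained |
|---|---|---|---|---|---|---|
| 3.5 (2) | 19% | 38% | 3.53 | 4.53 | 28% | 60% |
| 4.5 (2) | 10% | 22% | 4.51 | 5.12 | 14% | 77% |
| 5.0 (1.5) | 2% | 9% | 5.00 | 5.22 | 4% | 91% |

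Truncating out-of-range scores instead of capping them lowers the top gain from 28% to a little over 20%.

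**4. Effect on power.** Assume benefit proportional to starting pain, constant SD, and d = 1.2 without a cut. Then d with the cut = 1.2 × (mean with cut / mean without):

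- 1.2 × 4.53/3.53 = 1.54
- 1.2 × 5.12/4.51 = 1.36
- 1.2 × 5.22/5.00 = 1.25

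With 12 per group kept, power is 95%, 89% and 83%. Keeping 30 enrolled takes 30/0.60 = 50, 30/0.77 = 39 or 30/0.91 = 33 otherwise eligible subjects.

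**5. The same cut with a fixed pool.** If no extra subjects can be found, n per group falls to 12 × 0.60 = 7.2, 12 × 0.77 = 9.2 and 12 × 0.91 = 10.9. Power is then 77%, 79% and 79%, against 80% with no cut.

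**6. A harsher model, as a bound.** Suppose a share f shows no effect at all, the rest have d = 1.2, and the SD is unchanged. Then d = 1.2(1 − f):

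- f = 10%: d = 1.08, power 71.5%
- f = 20%: d = 0.96, power 61.3%
- f = 30%: d = 0.84, power 50.3%

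This overstates the loss for subjects at 1 or 2, who can still improve somewhat.

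**The case against.** The entry rules are not empty. Pain must be modified by jaw use, familiar pain must be reproduced on examination, and Sections 3 and 6 have the diagnosis confirmed again at Baseline. A pain-free person would probably not qualify, and nothing in the documents shows that very low scores would be common. Broad entry is defensible in a proof-of-concept study whose group size comes from a rule of thumb for pilot studies. The size of the problem rests wholly on assumed distributions. The gain from a cut is in raw points, whereas the plan's power is in SD units; if the SD of change rises with baseline pain, the standardised gain is smaller. With a fixed recruitable pool the gain disappears (step 5). No cut-off follows from the documents. All of this stands, and it limits the point to a recommendation.

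It does not remove the gap. The protocol states a superiority hypothesis on BPI severity, mild pain qualifies for entry, and under the assumptions above the direction of the effect is dilution.

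Four stronger readings are tempting, and the documents do not support them:

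- **Low-pain subjects cannot show a drug–placebo difference.** A subject at 2 can fall by 2 points or get worse.
- **Each subject must be able to improve by 1.2 SD.** That figure is a difference between group means.
- **The means and SDs for planning the next trial are distorted.** They are valid for the population enrolled and mislead only if the next trial uses different entry rules.
- **A null result could not be told apart from a floor effect.** Baseline BPI is collected for everyone, so a floor can be examined directly.

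**Conclusion.** The point holds as a design weakness that should be corrected; it is not an error in the sample-size calculation. What the documents establish is that no entry criterion sets a TMD pain level, that the BPI is absent from Screening, and that no rule uses the Baseline score. Subjects with mild or intermittent pain can therefore be randomised with little room to improve on the primary outcome.

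The magnitude is not established. Under the three assumed baselines, the share with low scores varies widely, and so does the benefit of a cut. The power gain depends on proportional benefit, constant SD, a reliability of 0.8 and enough extra screening to keep the planned enrolment.

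**What to change.** Add the BPI severity items to the Screening visit. Add an inclusion criterion requiring a pre-specified, modest minimum 4-item severity score for facial, jaw or TMD pain, with the cut-off chosen and justified by the sponsor. Keep the Baseline-visit BPI as the analysis baseline, so that the score used to select subjects is not the score from which change is measured.

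The direct cost is one short questionnaire at an existing visit and one eligibility line. The real cost is recruitment: at the illustrative cut of 3, about 9–40% of otherwise eligible subjects would fail, and the results would apply to a narrower population. The sponsor should confirm that the extra screening is feasible before adopting a cut.

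Sections 3 and 4 describe enrolment partly in the past tense. If it is complete, an entry rule is no longer usable. In that case, before unblinding:

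- commit to reporting the baseline BPI severity distribution by group;
- add baseline BPI as a covariate in the MMRM of the post-baseline scores;
- pre-specify a sensitivity analysis by baseline severity.

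These use data already collected and cost only analysis time. With about 12 subjects per group, the analysis by severity will be descriptive.

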4.2 Exclusion Criteria

Subjects that met any of the following criteria were not eligible for inclusion:

1. Lacking stable bilateral posterior occlusion;
2. Currently uses a complete maxillary or mandibular prosthetic denture;
3. Currently pregnant or plan to become pregnant;
4. Breastfeeding or plan to breastfeed;
5. Allergic to erenumab-aooe or any of the ingredients in Aimovig® (acetate, polysorbate 80, and sucrose);
6. Allergic to rubber or latex;
7. Currently undergoing TMD treatment elsewhere. Exception: patients undergoing TMD treatment involving the use of oral orthotics for a minimum of 3 months prior to Screening can be considered eligible for the study;

8. Started orthodontic treatment during the 3 months prior to Screening;
9. Currently included in other experimental protocols within the last 30 days or 5 half-lives before enrollment;
10. Having 8 or more migraine days during the past 4 weeks;
11. Started receiving massage, acupuncture or physical therapy treatment of the head, neck or shoulders during the previous 3 months prior to Screening;
12. History of unstable or acute severe non-head, neck or shoulder pain;
13. History of traumatic brain injury;
14. History of surgical treatment or recommended surgical treatment for TMD;
15. History of ongoing, unresolved disability litigation;
16. History of drug abuse;
17. Started treatment for moderate to severe sleep apnea requiring CPAP or oral mandibular repositioning appliance during the previous 3 months prior to Screening;
18. Anything that would place the subjects at increased risk or preclude the individual's full compliance with or completion of the study (e.g., medical condition, laboratory finding, physical exam finding logistical complication);
19. History of previously receiving erenumab-aoee or other anti-CGRP pathway therapies, including anti-CGRP and anti-CGRP receptor monoclonal antibodies and small molecule CGRP receptor antagonists (gepants);
20. History of chronic constipation and/or using medication associated with decreased gastrointestinal motility; and
21. History of uncontrolled hypertension or risk factors for hypertension.

4.3 Enrollment Procedures

Subjects were recruited using fliers and advertisements placed in the Indiana University (IU) School of Dentistry (IUSD) and other locations on the Indiana University Purdue University Indianapolis (IUPUI) campus including IU Health facilities. Fliers may also be posted on Facebook.

[name] may send approved study information to persons who may have TMD and he may also mention the study during planned radio interviews about TMD. [name] website will not mention research.

Persons responding to an advertisement will be given a brief description of the study and asked a series of questions related to the inclusion/exclusion criteria using an IRB approved phone script. Those who are interested and appear to meet the study requirements will be scheduled for a screening visit at the Oral Health Research Institute (OHRI).

Additionally, contact information was obtained from Regenstrief for IU Health patients who have indicated they have TMJ problems and are willing to be contacted for future studies. Once contact information was obtained, the OH study coordinator contacted the potential subjects by telephone to see if they were interested in attending a screening visit.

5. Treatments

5.1 Study Treatments

Investigational drug: erenumab-aooe (EREN) 140 mg, for s.c. injections, provided by Amgen

Placebo: liquid placebo (EREN-P), for s.c. injections provided by Amgen

Amgen provided the active and placebo free of charge through the Investigator Sponsored Studies (ISS) Program (CAMG334AUS01T).

5.2 Treatment Arms

Subjects were assigned at baseline to one of the two treatment arms:

- Arm A: erenumab-aooe (EREN) 140 mg s.c. administered every four weeks for a total of five treatments
- Arm B: placebo (EREN-P) s.c. administered every four weeks for a total of five treatments

